# Amendment history

Amendment No.	Protocol Version No.	Date issued	Author(s) of changes	Details of Changes made			
1	2	19.7.19	DW	Wording of SAE reporting changed to reflect comments from external scientific review by GD.  Wording of consent process changed to reflect comments from external scientific review by GD.			
2	3	3.9.19	DW	In response to comments from UoL sponsorship committee the following changes were made to the protocol:  1. Modification of the method of identifying patients whose samples had been run on FAPP to research team; handwritten logbook replaced with FAPP computer log.  2. Additional comment in consent section to account for the situation where consent is not subsequently obtained for a sample that has been run on FAPP.  3. Extra detail in the explanation of why FAPP may be superior to current lab methodology – specific mention of range of pathogens detected in addition to comments on speed.			
3	4	16.9.19	DW	In response to comments from UoL sponsorship committee (deputy chair) the following changes were made to the protocol:  1. Additional comments throughout to account for the situation where consent is not subsequently obtained for a sample that has been run on FAPP.  2. In the 'Participant Confidentiality' section additional information is added to explain the security measures pertaining to the storage of patient identifiers on the FAPP computer log.			

4	5 10	0.2.20	DW	
 
In response to NHS ethics review (email 23.1.20) the following amendments have been made:
 
The exclusion criterion relating to antibiotic administration has been modified to clarify the term "this episode of HAP".
 
The following sentence "No samples or parts thereof will be stored by the HAPOSS study" has been added at the end of the paragraph called "Risks".
 
In the section 'Consent' the process relating to registering a sample on the FAPP machine and the details stored in the FAPP sample log have been clarified.
 
Clarification of the security procedures relating to the study data base and its accessibility from a University laptop has been added in the section "Risks".
 
The previous paragraph titled anonymisation has renamed pseudoanonymisation and has been modified to clarify the process of assigning pseudoanonymised study numbers.
 

---	------	--------	----	--

# Synopsis

Study Title	H ospital A cquired P neumonia O bservational S tudy of S putum (HAPOSS)				
Trial Design	Observational cohort study				
Trial Participants	Adults (≥ 16 years old) diagnosed with hospital acquired pneumonia (HAP)				
Planned Sample Size	100 patients.  This pragmatic sample size reflects the need to recruit across different hospital wards and to detect a comprehensive range of pathogens.  We will present summary statistics. We will not conduct inferential testing.				
Follow-up duration	Once a patient has consented to the study there is no further follow-up.				
Planned Study Period	There will the	We aim to test 100 patient samples over 8 months.  There will then be a 4 month period during which we will analyse the results and generate a modified HAP treatment guideline for use in a future feasibility study and clinical trial.			
Objective	To determine the range and relative frequency of pathogens detected by the BIOFIRE FILM ARRAY PNEUMONIA PANEL when analysing sputum samples from patients with HAP.				
Investigational Device	Device	Pneumonia panel test kits – run on the BIOFIRE FILM ARRAY platform. This is a small, self-contained, close to patient platform for molecular microbiological testing of clinical specimens.			
	Sample type	Sputum			
	Sample volume	200μL			
	Sample preparation	Sample preparation is very simple and takes approx. 2 mins A sterile, absorbent, swab-on-stick is swirled around the sputum sample and absorbs a standard volume. Each test kit comes with the swab, test cartridge and two reagents.			
	Test run time	75 mins			

# **Background**

This study is the first part of a planned series of studies aimed at improving the outcome for patients who develop hospital-acquired pneumonia (HAP).

Pneumonia is a form of severe lung infection and we diagnose hospital-acquired pneumonia (HAP) if it develops in a patient who has been in hospital for greater than 48 hours - having been admitted for some other reason e.g. hip-replacement.[1] To meet the definition the patient must not have had any pneumonia symptoms when they were first admitted to hospital. The reason doctors differentiate HAP from pneumonia that develops outside of hospital (community-acquired pneumonia, CAP) is that we believe the bacteria responsible for HAP are often different to those causing CAP, necessitating different antibiotics. For that reason, a patient admitted from the community with pneumonia who has had a prior admission to hospital within the last 14 days, is also classified as having HAP, the rationale being that during their prior hospital admission they may have become 'colonised' with hospital type bacteria.[2]

HAP occurs in all hospitals – acute hospitals, paediatric, women's, neurological, cardiac or cancer hospitals.[3] HAP occurs on all wards, however there is an association with age, being more common in the elderly and in those with comorbidities such as cardiac, respiratory and neurological problems. It is a common post-operative complication and is associated with socioeconomic deprivation.[4]

The incidence of HAP is higher than all other Healthcare Associated Infections (HCAIs).[5] Moreover, it is responsible for more deaths than any other HCAI with an in-patient mortality of over 25%.[6]

Due to this potential for severity, there is pressure to administer antibiotics promptly following diagnosis. Since sputum cultures take on average 3 days to determine the cause of HAP, the initial antibiotic choice is a best guess as to the likely cause. There have been very few quality studies to help determine what the likely causes are and so our treatment guidelines extrapolate from studies of another type of pneumonia called ventilator-acquired pneumonia (VAP) — which develops in patients who are on ventilators in intensive care. VAP is associated with a wide range of bacteria but particularly Gram-negative bacteria and bacteria that are resistant to standard antibiotics. For this reason, it is current practice to administer two, extended-spectrum antibiotics to all patients with HAP.[1]

There are inherent problems with this empirical (best-guess) approach to antibiotic prescribing for HAP. First, the guess might be wrong and the antibiotic chosen might not kill the bacteria. Secondly, extended-spectrum antibiotics are associated with complications such as *Clostridium difficile* diarrhoea and thirdly, they are responsible for driving anti-microbial resistance.[7]

Ideally, we would use a test that could identify the cause of a patient's HAP before the first dose of antibiotics so we can get the choice right first time. The characteristics of such a test are that it would need to be able to detect all the relevant bacteria that cause HAP and the presence of any antimicrobial resistance genes. However, respiratory viruses are not currently part of our standard testing despite increasing evidence of their involvement in HAP.[8,9] Moreover there are a growing number of studies demonstrating nosocomial transmission of respiratory viruses such as influenza. The ideal HAP microbiology test would therefore not only be quick but also would test for both bacteria, resistance and detect viruses. There are no guidelines as to how soon after a diagnosis of HAP antibiotics ought to be administered but in CAP there is evidence to suggest 4 hours is the longest a patient ought to wait – so extrapolating this to HAP the ideal test would deliver an answer within 4 hours.[1]

The only commercially available platform to test for pneumonia specific pathogens and provide results within 4 hours is the BIOFIRE® FILMARRAY® Pneumonia Panel Plus (FAPP for short). This CE marked, United States Food and Drug Administration (FDA) approved near patient test can simultaneously detect 18 bacterial and 10 viral causes of HAP and the presence of 7 antimicrobial resistance genes. Sample preparation takes 2 minutes, requires no expertise and results are available in 75 minutes. https://www.biomerieux-diagnostics.com/biofire-filmarray-pneumonia-panel

Such a comprehensive, rapid test could dramatically change the way we manage HAP but before it is widely implemented, we must address questions relating to the interpretation of results and health economics within the NHS setting.

Ultimately, these questions will be answered by a large scale, randomised controlled trial of usual care versus management supported by this new test. However, such a trial will require a modified treatment guideline to inform the management of the patients in the intervention arm. This new guideline will help clinicians decide which antibiotic to prescribe their patient based on the bacteria and or viruses detected from the patient's sputum by the FAPP. This modified guideline should be informed by preliminary data demonstrating the likely pattern of bacterial, viral and resistance detections in the context of HAP. This study will generate the data required to create an antibiotic guideline based on FAPP results for use in local trusts participating in future trials of FAPP based management.

#### Aim

The aim of this study is to use a new diagnostic test to observe the range of bacteria and viruses identified from the sputum of patients with hospital Acquired Pneumonia (HAP) – and to use these observations to inform the design of a modified HAP treatment guideline for use in future trials.

# **Study Design**

# Summary

HAPOSS is a small, pragmatic observational study aimed at supporting future clinical trials. We will analyse a small ( $200\mu L$ ) sub-sample of each patient's sputum with a new diagnostic test called the FAPP. The remainder of the sputum sample will be processed normally and the results made available to clinicians in the usual manner but the results of the new test will be stored and analysed retrospectively. Once 100 samples have been through the FAPP we will invite a panel of experts to review the results from the new test and decide on a modified antibiotic prescribing guideline for use in future trials. An example of the readout of the FAPP is provided with this application.

We will not store any samples and participants will have just a single study visit by the research team, to obtain consent, there are no additional study visits. The study will recruit for 8 months at Aintree Hospital and the Royal Liverpool Hospital; there will then be 4 months of analysis and study close will be at 1 year.

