#### **Exclusion**

- Intention is to palliate rather than cure
- Non-English speaking
- Patients from whom a sputum sample cannot be obtained within 6 hours of the administration of the first dose of antibiotics for this episode of HAP.\*

\*For the purposes of this protocol, if the patient has had prior instances of HAP during the same or a recent admission, a new episode of HAP is defined as occurring following a 48 hour cessation of prior antibiotics. In that circumstance a patient will be eligible for HAPOSS if a sputum sample can be obtained within 6 hours of the first dose of antibiotic for this new HAP episode.

In the circumstance where a patient is diagnosed with HAP whist receiving antibiotics for a non-respiratory infection e.g. cellulitis, if the HAP diagnosis leads to a change in the antibiotic prescription to cover the HAP then that patient will be eligible for recruitment to HAPOSS if the sputum sample was obtained within 6 hours of the first dose of the new/additional antibiotics for HAP. If the diagnosis of HAP does not result in a change in antibiotic then the patient is in-eligible.

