#### Consent

The clinical team will obtain a single, clinically indicated sputum sample, as per usual care, and that sample will be immediately sub-sampled and run through the FAPP prior to being sent onwards, as usual, to microbiology. The data from the sample will be stored and the clinical team will have no access to this.

The patients' sample will be logged in the FAPP machine by means of a unique, 5-digit 'sample id'. Sample ids will consist of a site prefix followed by 3-digit consecutive sample numbers. For example, at Aintree all sample ids will have the prefix 01 and at the Royal Liverpool all sample ids will have the prefix 02 such that the first sample run at Aintree will be 01001 and the first at the Royal will be 02001 – the second Aintree sample will be 01002 and the second Royal sample will be 02002. The FAPP computer that holds this data will be password protected such that only members of the research team will be able to access this information. This FAPP log will be checked daily by the research team and new potential participants will be approached by the research team as soon as is practically possible. During this visit consent, or assent from a consultee will be obtained to analyse the stored sample data and for access to the standard medical record. In the situation where a patient declines consent or the consultee declines assent then the patient's data will not be included in the study.

Delivering interventions in an emergency setting makes HAP studies difficult and explains why there are so few. HAP has an inpatient mortality of over 25% and so it is important that research studies do not introduce undue delays to the clinical processes. Patients with HAP are more likely to be elderly and to have underlying cognitive impairment such as dementia. Moreover, HAP itself can cause transient delirium that impairs capacity. HAP occurs at any time of day and on any day of the week.

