The above consent process represents a hybrid between a 'research without prior consent' model to process the sputum in the FAPP machine and a standard consent model with respect to the use and storage of data obtained from the analysis of the sputum. The 'research without prior consent model' is used frequently in intensive care and emergency scenarios where the delivery of the intervention is time critical. There are very limited risks associated with testing the sputum sample and so this model will place minimal burden on patients. Recent studies have revealed that patients and families are keen to embrace such consent models in order to conduct research aimed at improving outcome in HAP.[10]

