# **Number of participants**

The sample size is pragmatic. Our recent audits of HAP cases demonstrate that Aintree hospital makes approximately 100 HAP diagnoses per-month with a slight seasonal bias towards an increase incidence in the winter. The Royal Liverpool has very similar rates. At both sites the rate of acquisition of sputum samples in routine clinical practice is 20%. Therefore, it there are 200 cases per month across both sites and sputum is acquired from 20% this means there will be 40 samples which could be tested per month. Assuming a 30% recruitment rate, this implies 12 samples per-month across the two sites. At this rate, our target of testing 100 samples will take approximately 8 months. This will enable us to recruit through a winter and into the summer to cover any seasonal variation in detections. Both hospitals are similar in terms of services, populations and protocols (and are now part of same trust) there is no scientific reason to insist on balanced recruitment. Recruitment will therefore continue until the target of 100 is reached.

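### The target of 100 is stated in patients in one place and in samples tested before consent in others, so the plan may deliver fewer than 100 analysable patients

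*Protocol*

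**What the plan says.** The Synopsis gives the planned sample size as 100 patients and justifies it thus: "This pragmatic sample size reflects the need to recruit across different hospital wards and to detect a comprehensive range of pathogens". Under the planned study period, the same table changes the unit: "We aim to test 100 patient samples over 8 months". The Study Design summary sets the point at which the guideline panel is convened: "Once 100 samples have been through the FAPP we will invite a panel of experts to review the results from the new test". The section on number of participants again counts tests: "our target of testing 100 samples will take approximately 8 months". It then says that recruitment goes on until the target of 100 is met, without naming the unit.

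Testing comes before consent. The consent section says: "The above consent process represents a hybrid between a 'research without prior consent' model to process the sputum in the FAPP machine". Under Screening and eligibility, the clinical team decides whether to run the FAPP, and the research team confirms eligibility only afterwards, before consent.

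Three routes then remove patients already tested:
- Refusal: "In the situation where a patient declines consent or the consultee declines assent then the patient's data will not be included in the study".
- Refusal by a patient who regains capacity, which overrides a consultee's earlier assent (section on patients without capacity).
- Withdrawal, after which the FAPP record is deleted from the study database (Withdrawal of participants).

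**The concern.** In most studies, patients and samples tested would be interchangeable labels. Here they are not, because the test is done first and the right to use its result is settled later. A count of runs includes people who will never be in the dataset, and the protocol neither allows for that loss nor says that lost runs are replaced.

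The count decides when recruitment ends and when the panel sits. The panel's product is an antibiotic guideline for use in later trials, built on which pathogens were seen and how often. Since no samples are stored, a smaller denominator cannot be made up later from retained material.

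The 30% recruitment rate does not settle the matter, because the protocol does not say whether it is the share of available samples that reach the FAPP, the share of patients who consent, or both combined.

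**Working it through.** **1. The plan's own accrual figure** (Number of participants). Inputs: 200 cases per month over two sites, sputum from 20%, recruitment rate 30%.
- 200 × 0.20 = 40 samples available per month
- 40 × 0.30 = 12 per month
- 100 / 12 = 8.33 months, stated as approximately 8. The figure reproduces.

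**2. What 100 means under each reading.** Let c be the share of runs that prove eligible, consented and not withdrawn.
- *100 runs* (Study Design summary, and the literal target in Number of participants): analysable patients = 100 × c. This equals 100 only if c = 1. If patients are independent and c = 95%, the chance that all 100 are retained is 0.95^100 = 0.6%.
- *100 recruited patients* (Synopsis sample size, and one reading of the continue-to-100 sentence): there is no shortfall, but runs needed = 100 / c, so the panel trigger of 100 runs is met before the sample size is.

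The sections agree only if no run is lost.

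**3. Size of the gap.** The document gives no value for c, so I assume 70% to 90%. Runs are rounded up, and the pace is taken as 12 runs per month.

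| c | Patients from 100 runs | Runs for 100 patients | Months at 12 runs per month |
|---|---|---|---|
| 100% | 100 | 100 | 8.3 |
| 90% | 90 | 112 | 9.3 |
| 80% | 80 | 125 | 10.4 |
| 70% | 70 | 143 | 11.9 |

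The protocol plans 8 months of recruitment, 4 of analysis and closure at 12. On these assumptions, 9.3 to 11.9 months of recruitment would leave 2.7 to 0.1 months for analysis.

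The months column applies if the 12 per month are runs. If the 12 are already consented patients, 100 patients arrive in 8.3 months as planned, but the 100-run trigger comes earlier than that.

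**4. What a smaller denominator costs.**
- Upper limit of the two-sided exact 95% interval for a pathogen never seen, 1 − 0.025^(1/n): 3.6% at n = 100 and 5.1% at n = 70.
- Chance of seeing at least once a pathogen present in 2% of patients, 1 − 0.98^n: 87% at n = 100, 84% at n = 90 and 76% at n = 70.
- Approximate 95% half-width for a 10% detection frequency, 1.96 × √(0.1 × 0.9 / n): 5.9 points at n = 100 and 7.0 at n = 70.

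**The case against.** The strongest reply is that this is loose wording and not a shortfall. The quoted trigger sentence says when the panel is invited, not when recruitment stops. The rule on stopping is in the sample-size section, follows a calculation that already includes a recruitment rate, and speaks of recruitment continuing to 100. Read with the Synopsis, that can mean 100 consented patients. The safety section also says that FAPP results stay unavailable to the research team until the last participant's disease episode is over, which makes an early panel review unlikely. The study claims no inference, sets no precision or detection target and calls its size pragmatic, so none of the losses above breaches a stated requirement.

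Much of this stands. A reader might infer that recruitment certainly stops at 100 runs, so that fewer than 100 patients is a sure result. The text does not establish that. But the only target the sample-size section names is samples tested, so the recruited-patient reading is possible without being clear. Where it is adopted, the panel trigger no longer matches. The safety statement limits when results may be seen, but does not say which count closes recruitment.

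Two further inferences are not supported:
- That test kits are under-planned: the protocol states no kit number that could be too low.
- That some patients will be counted twice: the exclusion section says "a new episode of HAP is defined as occurring following a 48 hour cessation of prior antibiotics", which makes patients with earlier episodes eligible. Re-enrolling someone already in the study is merely not barred.

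**Conclusion.** The inconsistency of unit holds and can be checked from the text alone. The Synopsis sample size, the tested-sample target and the panel trigger cannot all be met at 100 unless every run is eligible, consented and retained, and nothing in the plan covers the difference.

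The size of any shortfall is not known. It rests on an assumed retention of 70% to 90%, under which 100 runs yield 70 to 90 patients. The detection figures at 70 patients are the unfavourable end of that range; at 90 the loss is small. Data handling is not in question, since the rules for excluding refusals and withdrawals are clear.

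Severity is moderate. The study is descriptive and its size pragmatic, so the loss of precision is tolerable. However, the ambiguity bears directly on when recruitment ends, when the panel meets and what denominator the guideline rests on.

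**What to change.** In the Synopsis, the Study Design summary and the section on number of participants, define the target in one unit: 100 different eligible patients with consent or assent and a valid FAPP result. Tie both the end of recruitment and the panel meeting to that count. Requiring different patients also settles the minor question of repeat episodes. State whether the 30% covers testing, consent or both, and restate the recruitment period to match.

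Alternatively, keep 100 runs as the target, change the Synopsis accordingly, and state the number of analysable patients expected from them.

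The first option costs a wording amendment and, at the assumed retention, 12 to 43 more runs (112 − 100 to 143 − 100), with a longer recruitment period if the 12 per month are runs. The second costs only the wording and a less favourable stated number.

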#### Intervention

The new test is the BIOFIRE® FILMARRAY® Pneumonia Panel Plus (FAPP for short). The FAPP is a CE marked, United States Food and Drug Administration (FDA) approved near patient test that can simultaneously detect 18 bacterial and 10 viral causes of HAP and the presence of 7 antimicrobial resistance genes. Sample preparation takes 2 minutes, requires no expertise and results are available in 75 minutes. https://www.biomerieux-diagnostics.com/biofire-filmarray-pneumonia-panel

